Pilot Study of Natriuretic Versus Standard Doses of Mineralocorticoid Receptor Antagonists in
Heart Failure and Loop Diuretic Resistance in Outpatients

NCT: 02585843

Date 8/30/2015

Study Design

We conducted a pilot, prospective, single-center, double-blind, randomized, placebo controlled trial assessing the effects of high dose spironolactone in addition to intensified loop diuretic therapy vs. standard medical therapy in outpatients with ADHF. Our primary outcome was defined as weight change over the seven day study period. Based on data from a non-randomized intervention study, we aimed to recruit a total sample size of 40 subjects to detect a difference in our primary outcome of weight loss of 1.5kg difference between treatment and control.

On Day 1, all potential subjects were evaluated with complete medical history and physical examination, review of home medications, measurement of vital signs and body weight with a calibrated scale, serum collection for basic metabolic panel, liver function test, biomarkers of congestion, and electrocardiogram. "Imminent hospitalization" was determined by two independent HF specialists to assess the need for hospitalization for intravenous diuretics. Home MRAs were discontinued and potassium supplementation held if baseline serum potassium was >4.0mmol/L. Beta-blockers, ACE-I or angiotensin II receptor blockers were continued at home dose. Loop diuretic dosage was increased by two-fold. Patients were seen at two office visits in total, baseline at day 1 and final visit on day 7. On day 3, participants had serum basic metabolic panel to assess potassium levels and renal function for safety assessment.

Intervention

Enrolled patients were randomly assigned in a 1:1 ratio to high-dose (100mg/day) or standard-dose (25mg/day) spironolactone treatment groups.

Randomization, Allocation and Blinding

Randomization was stratified by sex and EF<45% in blocks of size 4. 2 by 2 randomization was performed via computer model generated by a study investigator. Allocations were concealed via the locked research pharmacy and the research team was blinded to treatment arm. All treatment medications were labeled in a blinded fashion. Subjects received 2 capsules per day (if standard dose: 25mg and placebo, if high dose: two 50mg) dispensed in vials of 2 capsules.

Study Endpoints

The primary endpoint for the study was defined as change in total body weight at day 7 of the study period. Multiple secondary endpoints from day 1 to 7 were assessed. These included a) changes in dyspnea assessment scores; Visual Analogue Scale and 7-Likert scale, b) signs of congestion (i.e. JVP, peripheral edema and respiratory rales), c) 6MWT, d) serum and urinary creatinine, sodium, potassium and plasma aldosterone and renin activity and biomarkers of congestion and neurohormonal activation, e) furosemide equivalent of treatment loop diuretics doses, e) hospitalization at 30-, 60- and 90-days.

Six-minute walk test was performed per American Thoracic Society guidelines, along with Borg scores for dyspnea and fatigue at day 1 and 7. Serum and urinary creatinine, potassium, and sodium, plasma aldosterone and renin activity, and pro-BNP were assessed at days 1 and 7.

Other biomarkers of peripheral congestion (CD146), inflammation (interleukin-6, tumor necrosis factor- α , endothelin-1) oxidative stress (isoprostane) and endothelial activation (vascular cell adhesion molecule-1) were assessed at day 1 and 7 and analyzed by ELISA or LC-MS.

A data monitoring committee of two independent cardiologists was established to evaluate safety, with a pre-specified stopping rule for harm but not for efficacy. Safety endpoints included changes in serum creatinine levels, eGFR, and the incidence of hyperkalemia during the 7 day treatment period. Safety was assessed by tracking adverse events including new or worsening renal dysfunction, and hyperkalemia. Serious adverse events were defined as death and all-cause hospitalization.

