Pilot Study of Natriuretic Versus Standard Doses of Mineralocorticoid Receptor Antagonists in
Heart Failure and Loop Diuretic Resistance in Outpatients

NCT: 02585843

Date 8/30/2015

Study Endpoints

The primary endpoint for the study was defined as change in total body weight at day 7 of the study period. Multiple secondary endpoints from day 1 to 7 were assessed. These included a) changes in dyspnea assessment scores; Visual Analogue Scale and 7-Likert scale, b) signs of congestion (i.e. JVP, peripheral edema and respiratory rales), c) 6MWT, d) serum and urinary creatinine, sodium, potassium and plasma aldosterone and renin activity and biomarkers of congestion and neurohormonal activation, e) furosemide equivalent of treatment loop diuretics doses, e) hospitalization at 30-, 60- and 90-days.

Six-minute walk test was performed per American Thoracic Society guidelines, along with Borg scores for dyspnea and fatigue at day 1 and 7. Serum and urinary creatinine, potassium, and sodium, plasma aldosterone and renin activity, and pro-BNP were assessed at days 1 and 7. Other biomarkers of peripheral congestion (CD146), inflammation (interleukin-6, tumor necrosis factor- α , endothelin-1) oxidative stress (isoprostane) and endothelial activation (vascular cell adhesion molecule-1) were assessed at day 1 and 7 and analyzed by ELISA or LC-MS.

A data monitoring committee of two independent cardiologists was established to evaluate safety, with a pre-specified stopping rule for harm but not for efficacy. Safety endpoints included changes in serum creatinine levels, eGFR, and the incidence of hyperkalemia during the 7 day treatment period. Safety was assessed by tracking adverse events including new or worsening renal dysfunction, and hyperkalemia. Serious adverse events were defined as death and all-cause hospitalization.

Statistical Analysis

Statistical analyses were performed using SPSS version 23. Continuous variables are presented as mean \pm SD (or median with IQR if not following normal distribution) and categorical variables were summarized as counts (percentages). The χ^2 test or Fisher's exact test (when cell counts were small) were used to compare categorical variables. Paired t-tests and the Wilcoxon rank sum test was used to compare continuous variables pre vs. post intervention within treatment arms. ANOVA was performed to compare continuous variables post-intervention. P< 0.05 considered statistically significant for all comparisons.

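### The between-arm analysis of 7-day weight change names no covariate, so the Day 1 home loop diuretic dose goes unused, a possible loss of precision but not a bias

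*Protocol*

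**What the plan says.** The title places the trial in "Heart Failure and Loop Diuretic Resistance in Outpatients". The Protocol's Study Design section describes the comparison as high-dose spironolactone added to "intensified loop diuretic therapy vs. standard medical therapy in outpatients with ADHF", and does not mention resistance. The only entry judgement described was "determined by two independent HF specialists to assess the need for hospitalization for intravenous diuretics".

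Day 1 includes a "review of home medications", and then "Loop diuretic dosage was increased by two-fold". I read this as doubling the dose the patient was taking at home.

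Loop dose comes back only as a secondary endpoint, the "furosemide equivalent of treatment loop diuretics doses" (Protocol and SAP, Study Endpoints). It plays no part in allocation: "Randomization was stratified by sex and EF<45% in blocks of size 4" (Protocol, Randomization, Allocation and Blinding).

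For the between-arm comparison the SAP's Statistical Analysis section says "ANOVA was performed to compare continuous variables post-intervention". It names no covariate: not home dose, baseline weight, sex or EF.

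**The concern.** Doubling makes each patient's step-up in mg equal to the home dose. Two patients in the same arm can therefore get very different amounts of additional loop diuretic over the week in which weight is the primary outcome. If home dose predicts weight change, that variation sits in the residual error of an unadjusted ANOVA and widens the interval around the treatment difference. Conditioning on a baseline value that is already to hand would remove part of it.

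With 20 patients per arm and a target difference of 1.5 kg, there is little precision to give away. Home dose would also help a reader see what kind of patients were enrolled, since the title names a population that the design text does not define.

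**Working it through.** **The plan's own figure.** The Protocol gives a total of 40 patients, 1:1, for a 1.5 kg difference. It states no SD, power, sidedness or dropout, so the figure cannot be reproduced. Solving backwards with the normal approximation, assuming 80% power, two-sided 0.05 and no dropout:

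SD = 1.5 × √(20/2) / (1.960 + 0.842) = 4.743 / 2.802 = 1.69 kg.

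Other conventions give other values: 1.91 kg (80%, one-sided), 1.46 kg (90%, two-sided) and 1.62 kg (90%, one-sided). I use 1.69 kg for illustration only.

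**Effect of adjusting for home dose.**

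- Inputs from the documents: N = 40, 20 per arm, difference 1.5 kg, significance level 0.05.
- Assumed: r, the correlation of (log) home dose with 7-day weight change, from 0 to 0.5. No value is given.
- One baseline covariate multiplies the residual variance by 1 − r².
- Chance imbalance in that covariate costs, on average, a factor (N − 3)/(N − 4) = 37/36 = 1.028.
- Net variance factor = (1 − r²) × 37/36. It does not depend on the SD.
- Equivalent N = 40 / net factor.
- Power uses the noncentral t: 38 df unadjusted, 37 df adjusted.

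| r | Net variance factor | Change in variance | Change in SE | Equivalent N | 95% CI half-width, SD 1.69 | Power, SD 1.69 |
|---|---|---|---|---|---|---|
| unadjusted | 1 | – | – | 40 | 1.08 kg | 77.9% |
| 0 | 1.028 | +2.8% | +1.4% | 38.9 | 1.10 kg | 76.8% |
| 0.1 | 1.017 | +1.7% | +0.9% | 39.3 | 1.09 kg | 77.2% |
| 0.2 | 0.987 | −1.3% | −0.7% | 40.5 | 1.08 kg | 78.4% |
| 0.3 | 0.935 | −6.5% | −3.3% | 42.8 | 1.05 kg | 80.5% |
| 0.4 | 0.863 | −13.7% | −7.1% | 46.3 | 1.01 kg | 83.6% |
| 0.5 | 0.771 | −22.9% | −12.2% | 51.9 | 0.95 kg | 87.4% |

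Break-even: 1 − r² = 36/37, so r² = 1/37 = 0.027 and r = 0.16.

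**Dependence on the SD.** Power does depend on it. With an SD of 2.5 kg, unadjusted power is 45.6%, and adjusted power is 44.6% at r = 0, 48.0% at r = 0.3 and 55.8% at r = 0.5. The proportional changes in variance stay the same.

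**Reading r with other covariates present.** The table treats home dose as the only covariate. Once baseline weight, sex and EF are in the model, what matters is the correlation left after those are accounted for, which may be smaller.

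**The case against.** The strongest objection is that nothing in the documents shows home dose to predict weight change. A higher home dose means a larger step-up in mg, but it may also mark a patient who responds less to loop diuretics. These pull in opposite directions, and r could be near zero. This stands. It is why the gain is conditional, and why the range above has to include values at which adjustment loses slightly.

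It can also be said that home dose has no special claim, because the ANOVA omits baseline weight and the stratification factors too, and a 40-patient pilot should carry few covariates. This stands as well: home dose belongs in a short list, not alone or ahead of the others.

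Three stronger readings are tempting, and the documents do not support them.

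- **Bias.** A reader might infer that unequal home doses bias the comparison. Home dose is fixed before randomization, so it is balanced in expectation.
- **Chance imbalance as a second harm.** A reader might count a chance difference in home dose between arms in addition to the wider interval. That variation is already in the unadjusted standard error, so the two are one loss.
- **A diluted effect.** A reader might infer that patients who were not resistant entered and diluted the treatment effect. Neither public document has an eligibility section, so they cannot show whether entry required resistance. They give no proportion of responders to the doubled loop dose. The 1.5 kg target comes from a non-randomized study that may already average over such patients, and covariate adjustment would not remove them in any case.

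**Conclusion.** The point holds as a matter of efficiency. The planned weight comparison leaves out a pre-randomization variable that bears directly on background diuretic treatment and should be available from Day 1. Whether this costs precision depends on r. Below about 0.16 it costs nothing, and adjustment would be slightly harmful. At r = 0.3 to 0.5 the standard error would be about 3% to 12% smaller, worth about 3 to 12 patients. These figures assume 40 analysed patients, a linear relation with home dose and no other covariate in the model. The validity of the unadjusted comparison is not in question.

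On the population, the documents support a limited statement. Resistance appears only in the title and is not defined, while the design text describes outpatients with ADHF. This is a matter of how conclusions are worded, and it does not show that the wrong patients were enrolled. Home dose by arm would describe the patients but would not by itself prove resistance, which also needs a measure of response. Nothing here is a comment on the choice of diuretic dose.

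**What to change.** In the SAP's Statistical Analysis section, prespecify the between-arm comparison of 7-day weight change as an ANCOVA with treatment arm and four covariates: baseline weight, sex, the EF stratum, and log Day 1 home furosemide-equivalent dose. Report the adjusted difference with its 95% CI.

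Use the home dose from the Day 1 review, not the treatment dose listed as a secondary endpoint, because the latter can be affected by what happens after assignment. On the log scale the home dose and the doubled dose differ only by a constant, so they carry the same information, and the log limits the influence of a few very high doses.

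Tabulate home dose by arm. State conclusions for outpatients with ADHF, unless entry actually required resistance; in that case, give the definition that was used.

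The cost is SAP wording plus conversion of the recorded home doses. Residual degrees of freedom fall from 38 to 34 (40 − 2 − 4). If home dose does not predict weight change, its inclusion loses a little precision, about 3% of the variance at r = 0. The stated population becomes narrower than the title suggests.

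### Sex and EF group stratify the randomization but appear in no between-arm analysis; naming them in the primary model costs two degrees of freedom and gains power if they predict weight change

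*Protocol*

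**What the plan says.** The Protocol, under Randomization, Allocation and Blinding, states: "Randomization was stratified by sex and EF<45% in blocks of size 4". Two binary factors give four strata. Patients are "randomly assigned in a 1:1 ratio", and the Study Design section says "we aimed to recruit a total sample size of 40 subjects" in order "to detect a difference in our primary outcome of weight loss of 1.5kg difference between treatment and control".

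The SAP, under Study Endpoints, fixes the outcome: "The primary endpoint for the study was defined as change in total body weight at day 7 of the study period". Under Statistical Analysis, the only between-arm method for a continuous outcome is this sentence: "ANOVA was performed to compare continuous variables post-intervention". Categorical outcomes get chi-square tests, or Fisher's exact test when counts are small.

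Neither sex nor EF, nor any other covariate, is named in any of these analyses. The primary endpoint has no model of its own, and the terms of the ANOVA are not listed.

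**The concern.** Blocking within strata forces the arms to be nearly balanced on sex and EF group, so differences between strata largely drop out of the treatment contrast. A model with arm alone does not know this. It leaves the between-stratum variation in its residual and reports a standard error larger than the true sampling variation of the estimate. If the strata are prognostic, the test rejects too rarely under the null and has less power than the design could deliver.

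There is no added false-positive risk and no bias. What is at stake is power that the design has already paid for, in a trial with about 20 patients per arm. A second, smaller matter is that a model with unstated terms allows the choice to adjust or not to be made once the results are known.

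**Working it through.** **Inputs from the documents.** N = 40, 1:1, so 20 per arm; target difference 1.5 kg; four strata; blocks of 4; significance at 0.05 (sidedness not stated, two-sided assumed).

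**Inputs not in the documents, so assumed.** SD of weight change; the share of its variance explained by sex and EF group (R²); 65% male; 50% with EF<45%; all 40 patients analysed.

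**Step 1: the plan's own figure.** The sample size of 40 cannot be reproduced, because neither SD nor power is stated. It can be solved backwards. For 80% power by the normal approximation:

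SD = 1.5 / [(1.960 + 0.842) × √(2/20)] = 1.5 / (2.802 × 0.3162) = 1.69 kg

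The exact t-test gives 1.65 kg. The value 1.69 kg is used below, with 1.4 to 2.0 kg as a sensitivity range.

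**Step 2: the price of adjusting.** Two main effects take the residual degrees of freedom from 40 - 2 = 38 to 40 - 4 = 36. The critical t moves from 2.024 to 2.028. If the factors predict nothing, the noncentral t at SD 1.65 kg gives power of 79.8% instead of 79.95%, a loss of about 0.1 point.

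**Step 3: what adjusting can gain.** The residual SD becomes SD × √(1 - R²). At R² = 0.20 it is 1.69 × √0.80 = 1.51 kg, so the standard error falls from 1.69 × √(2/20) = 0.534 to 1.51 × √(2/20) = 0.478 kg.

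**Step 4: simulation of the actual design.** Small strata leave incomplete blocks, so balance is not exact. The design was therefore simulated: 20,000 trials per setting, permuted blocks of 4 within four strata, and total SD held at 1.69 kg. The sex and EF shifts were equal and chosen to give the stated R²: b = √[R² × 1.69² / (0.65 × 0.35 + 0.50 × 0.50)], which is 0, 0.55, 0.77 and 1.09 kg. Weight change was regressed on arm, with and without the two main effects.

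| R² | Power, arm only | Power, adjusted | Change (points) | Type I error, arm only |
|---|---|---|---|---|
| 0 | 77.8% | 77.3% | -0.5 | 5.2% |
| 0.05 | 77.9% | 79.3% | +1.4 | 4.6% |
| 0.10 | 78.7% | 81.6% | +2.9 | 3.9% |
| 0.20 | 80.1% | 86.0% | +5.9 | 3.2% |

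Adjusted type I error stayed between 4.8 and 5.2%. The Monte Carlo standard error of each power figure is about √(0.78 × 0.22 / 20,000) = 0.3 point, so the difference between -0.5 here and -0.1 in step 2 should not be read closely.

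**Step 5: the mechanism shows directly.** For the arm-only model, mean reported standard error against the actual SD of the estimate was 0.532 vs 0.537 kg (R² 0), 0.532 vs 0.526 (0.05), 0.533 vs 0.509 (0.10) and 0.533 vs 0.484 (0.20). At R² = 0.20 the reported error is too large by 0.533 / 0.484 = 1.10. The effective critical value is then 2.024 × 1.10 = 2.23, which on 38 degrees of freedom is a two-sided level of 3.2%, as simulated.

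**Step 6: sensitivity.** Over SDs of 1.4 to 2.0 kg, adjusting costs at most about half a point at R² 0 and gains 0.6 to 1.8 points at R² 0.05, 1.7 to 3.7 at 0.10 and 2.8 to 8.6 at 0.20. With 80% male and 70% EF<45%, the gains at SD 1.69 kg are 1.6, 2.6 and 6.3 points at R² 0.05, 0.10 and 0.20. A second simulation at SD 1.65 kg gave gains of 2.4 and 5.8 points at R² 0.10 and 0.20. Adding the sex-by-EF interaction brought nothing further under this additive model.

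**The case against.** Four arguments deserve weight.

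- **The SAP is silent; it does not exclude the factors.** A factorial ANOVA with arm, sex and EF group fits its sentence as well as a one-way ANOVA does. This stands: the fault is under-specification, and the power loss exists only if the model is arm-only. It is also why one sentence settles the matter.
- **Nothing in the documents says the strata are prognostic.** This stands too. R² = 0.20 requires each factor to shift weight change by 1.09 kg, which is 73% of the 1.5 kg target effect, and the extreme strata would differ by 2.18 kg. The gains at R² = 0.20 are therefore best read as an upper end, with R² from 0 to 0.10 (about -0.5 to +3 points) as the modest case. The asymmetry still favours adjusting, because the downside is half a point or less.
- **The SAP sentence leaves open whether the ANOVA is of change or of day-7 weight, and whether baseline weight is included.** True, and it needs its own answer. The figures here apply to weight change, the stated primary endpoint, and not to raw day-7 weight.
- **Both documents are written in the past tense.** If the analysis had already been run, adding the factors now would itself be post hoc. The documents do not settle this. It limits the pre-specification benefit but does not change which model suits the design.

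**Conclusion.** The point holds, as a free improvement. It is certain that both factors stratify the randomization and that the SAP names neither in any between-arm analysis. An arm-only test would be valid but conservative when the strata are prognostic, and its power does not fall as R² rises, so adjustment is a possible gain and not the repair of a shortfall. The size of that gain is uncertain: roughly 1 to 3 points at R² of 0.05 to 0.10 and about 6 at 0.20, against a loss of no more than about half a point if the factors predict nothing. These figures rest on an assumed SD of 1.69 kg, assumed R² and assumed stratum prevalences. No size is claimed for secondary or binary endpoints.

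**What to change.** Add one sentence to the SAP's Statistical Analysis section: the between-arm comparison of change in body weight at day 7 uses a linear model with arm, sex and EF group (<45% vs ≥45%) as main effects, without arm-by-stratum terms. Use the same model for the continuous secondary endpoints, for consistency. A stratified test for hospitalization is optional, since 40 patients over four strata average about 10 each.

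The cost is the wording and two residual degrees of freedom. No patients, visits or data are added, because both factors are recorded at randomization. If the analysis has already been run, report the adjusted result beside the existing one and state when each was specified.

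### The primary weight endpoint has no rule for heart failure admission or IV diuretics before day 7, so rescue weight loss can be credited to the assigned spironolactone arm

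*Protocol*

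**What the plan says.** The Protocol (Study Design) states the primary outcome as follows: "Our primary outcome was defined as weight change over the seven day study period". Study Endpoints, in both the Protocol and the SAP, repeats it: "The primary endpoint for the study was defined as change in total body weight at day 7 of the study period". Neither statement attaches a condition about events between day 1 and day 7.

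The Protocol (Study Design) describes the comparison as high-dose spironolactone plus "intensified loop diuretic therapy vs. standard medical therapy in outpatients with ADHF". It adds that imminent hospitalization "was determined by two independent HF specialists to assess the need for hospitalization for intravenous diuretics". It does not say whether this finding led to inclusion, to exclusion or only to a record.

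Hospitalization appears in two places, neither linked to the primary endpoint. It is a secondary endpoint at 30, 60 and 90 days, and it is a safety event: "Serious adverse events were defined as death and all-cause hospitalization".

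Office visits are on days 1 and 7 only. The sole scheduled contact between them is a day-3 blood test. The SAP (Statistical Analysis) compares arms by ANOVA on post-treatment values. It gives no estimand, no analysis set and no rule for weights taken after other treatment.

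**The concern.** IV diuretics lower the same quantity that the trial reads as benefit. Suppose a patient becomes more congested on the assigned oral regimen, receives IV diuretics and is then weighed on day 7. That patient may show a larger loss than one who did moderately well without rescue. Used as observed, the weight is a favourable result for the arm in which treatment failed.

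This is distinct from missing weights: here the weight exists, but another treatment produced part of it. At stake is the contrast the trial was sized for. If congestion failures are more frequent on standard dose, a real benefit of high dose is diluted. If they are more frequent on high dose, the benefit is exaggerated.

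**Working it through.** **Inputs from the documents.** Total sample size 40 with 1:1 allocation, so 20 per arm; target difference 1.5 kg; significance level 0.05 (taken as two-sided, since sidedness is not stated).

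**The plan's own figure.** The Protocol says "we aimed to recruit a total sample size of 40 subjects". The stated basis is a gap of 1.5 kg between arms. No SD or power is given, so 40 cannot be reproduced. The SD it implies is 1.5 × √(20/2) / (z for alpha + z for power):
- 80% power, two-sided: 1.5 × 3.162 / (1.960 + 0.842) = 1.69 kg
- 90% power, two-sided: 1.46 kg
- 80% and 90% power, one-sided: 1.91 and 1.62 kg

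I use 1.7 kg below, as an assumption.

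**Effect of one patient.** If a rescued patient loses L kg more by day 7 than without IV diuretics, the arm mean moves by L/20. Taking L = 3 to 5 kg (assumed; the documents give no figure):
- L = 3: 3/20 = 0.15 kg, and 0.15/1.5 = 10% of the target
- L = 5: 5/20 = 0.25 kg, and 0.25/1.5 = 17% of the target

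**Effect of an imbalance.** Let pH and pS be the proportions rescued on high and standard dose.
- Expected difference = 1.5 − (pS − pH) × L
- Each arm's variance = 1.7² + p(1 − p)L²

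For pH = 5%, pS = 20%, L = 4:
- Difference = 1.5 − 0.15 × 4 = 0.90 kg
- Variances = 2.89 + 0.76 = 3.65 and 2.89 + 2.56 = 5.45
- Standard error = √(9.10/20) = 0.675 kg
- Approximate power = 1 − Φ(1.96 − 0.90/0.675) = 27%

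Simulation (4,000 trials, mean losses 3.0 and 1.5 kg without rescue) gives about 25% for the t-test. Results at L = 4 kg, as the chance of a significant result favouring high dose:

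| Rescued, high vs standard | Mean difference | t-test on observed kg | Worst-rank rank-sum |
|---|---|---|---|
| 0% vs 0% | 1.5 kg | 78% | 76% |
| 5% vs 20% | 0.9 kg | 25% | 83% |
| 20% vs 5% | 2.1 kg | 86% | 19% |
| 5% vs 5% | 1.5 kg | 68% | 65% |
| 10% vs 10% | 1.5 kg | about 60% | about 55% |

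The simulated percentages vary by a point or two between runs. In the second and third rows the observed-weight analysis moves towards the arm with more failures. In the last two rows the mean difference is unbiased, and the cost is added variance, which the rank analysis does not recover.

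**The case against.** The strongest reply is that the documents are silent rather than wrong, and several stronger readings do go beyond them.

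- **That the plan scores weight regardless of what happened.** A reader might infer a deliberate rule from the unconditional wording, but none is written. Day 7 is an office visit, so a patient in hospital that day may have no study weight at all. That is a missing-data problem, equally unaddressed. Nor is there a success threshold: the endpoint is a mean change.
- **That the participants were judged close to admission, so early failure is the expected course.** The use made of the day-1 assessment is not stated and could have been exclusion. No 7-day admission rate is given.
- **That every hospitalization biases the result.** The mechanism applies only to admissions for congestion or to IV diuretic use. Admissions for hyperkalemia or renal dysfunction, which the plan also tracks for safety, need not remove weight.
- **That early hospitalization is recorded only as a safety event.** The 30-day secondary endpoint may include days 1 to 7; its starting point is not stated.

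A treatment-policy comparison of weight as observed is also legitimate if chosen openly, and worst rank answers a somewhat different question.

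These points limit the claim but do not remove it. Taken as written, the endpoint admits a post-rescue weight without qualification, and the planned ANOVA would then count rescue as benefit. In outpatients with ADHF who were assessed for this very need, the event is foreseeable even if its frequency is unknown.

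**Conclusion.** The concern stands as a gap that can produce a wrong result. The primary analysis has no rule for heart failure admission or IV diuretics before day 7, and using such weights as observed shifts the comparison in favour of the arm with more congestion failures.

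That such weights can enter unqualified follows from the text. The size does not: rescue rates, extra loss and SD are all assumed. A reader might infer from the 25% power figure that the trial is likely to miss a true effect. The documents do not support that, because the figure belongs to one assumed imbalance. The opposite imbalance inflates the difference to 2.1 kg, and equal rates leave it at 1.5 kg. The firmer statement is that, at 20 per arm, each rescued patient with 3 to 5 kg extra loss moves an arm mean by 10% to 17% of the target, so a few cases matter.

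**What to change.** State in both documents that a weight taken after heart failure admission or IV diuretics does not count as a favourable result. A workable rule is a worst-rank analysis: rank death, heart failure hospitalization or IV diuretics before the day-7 visit below all other outcomes, rank the remaining patients by day 1 to day 7 weight change, and compare arms with a rank-sum test. Report the observed kg difference beside it. At minimum, make this a pre-specified sensitivity analysis to the kg comparison. In either case, report early failures through day 7 by arm.

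The change is mainly wording, because all-cause hospitalizations are already tracked. The costs are:
- The rank analysis gives no single kg estimate.
- Power is slightly lower if failures are balanced (65% against 68% at 5% per arm).
- IV diuretics given without admission must be recorded, and hospitalizations must be classified as heart failure or other, blind to arm.

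Substituting the last weight before IV treatment is not recommended unless such weights already exist, since no weight is scheduled between days 1 and 7.

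### Potassium harm is counted only on the high side, low potassium and low sodium have no planned incidence by arm, and no blood pressure is stated after day 1

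*Protocol*

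**What the plan says.** The safety part of Study Endpoints, which has the same wording in the Protocol and the SAP, reads: "Safety endpoints included changes in serum creatinine levels, eGFR, and the incidence of hyperkalemia during the 7 day treatment period". Adverse events follow: "Safety was assessed by tracking adverse events including new or worsening renal dysfunction, and hyperkalemia". Then: "Serious adverse events were defined as death and all-cause hospitalization". Neither document names hypokalemia, hyponatremia or hypotension, and neither gives a limit for them. No limit is given for hyperkalemia either.

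The treatment changes are in the Protocol, under Study Design and Intervention:

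- "Loop diuretic dosage was increased by two-fold", with no difference between arms stated.
- "Home MRAs were discontinued and potassium supplementation held if baseline serum potassium was >4.0mmol/L". The potassium condition may govern the supplements only, or the home MRAs as well.
- "Enrolled patients were randomly assigned in a 1:1 ratio to high-dose (100mg/day) or standard-dose (25mg/day) spironolactone treatment groups".

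The measurements are as follows. For day 3: "On day 3, participants had serum basic metabolic panel to assess potassium levels and renal function for safety assessment". For the start and end of treatment: "Serum and urinary creatinine, potassium, and sodium, plasma aldosterone and renin activity, and pro-BNP were assessed at days 1 and 7". Serum potassium and sodium are also listed among the secondary endpoints. Vital signs are mentioned once, in the day-1 evaluation.

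**The concern.** The treatment plan can move potassium either way. Doubling the loop diuretic and withholding supplements tend to lower it; spironolactone tends to raise it, more so at the higher dose. The randomized contrast is therefore expected to shift events from one end of the potassium range to the other. The safety endpoints count only one end, and it is the end the high dose can worsen. A possible safety advantage of the high dose, fewer low values, would have no planned place in the results.

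Low sodium and hypotension are foreseeable when diuresis is intensified and ACE-I or ARB and beta-blockers continue, but neither has an incidence endpoint. For hypotension the measurement itself is not stated after treatment starts. What is at stake is a complete and balanced safety table in a pilot whose purpose includes judging whether a high dose is tolerable. The primary endpoint, weight change, is not affected.

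**Working it through.** **1. What is measured against what is counted**

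| Item | Measured after treatment starts | Planned incidence by arm |
|---|---|---|
| High potassium | Days 3 and 7 | Yes, as a safety endpoint |
| Low potassium | Days 3 and 7 | None stated |
| Low sodium | Day 7; day 3 if the metabolic panel reports sodium, as such panels usually do | None stated |
| Low blood pressure | None stated | None stated |

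The two laboratory rows lack only a planned count. The last row lacks a stated measurement as well.

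**2. Whether the SAP's methods supply the missing counts.** The Statistical Analysis section summarizes continuous variables by mean and SD, or median and IQR. It compares them before and after treatment by paired t-test or Wilcoxon test, and post-intervention by ANOVA. None of these gives the number of patients below a limit, and an arm mean can be unremarkable while individual patients are out of range. The chi-square and Fisher tests could be used for such a count, but the count is not defined.

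**3. Direction between arms**

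- Potassium: the higher dose of a potassium-retaining drug should give more high values and fewer low ones. The omitted event is one the high dose could reduce.
- Low sodium and hypotension: if 100 mg produces stronger natriuresis, these could be more frequent with 100 mg, and leaving them out would favor the high dose. The documents give no data, so the direction is not known.
- Loop doubling is stated without a difference between arms, so it makes these events foreseeable but does not itself create an imbalance.

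**4. What added counts could show.** The documents give no figure for these events. Their only sample-size figure is 40 in total, to detect 1.5 kg of weight loss. It cannot be reproduced, because SD and power are not stated, and this point does not rest on it. At 1:1, 40 gives 20 per arm.

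- No events in an arm: two-sided exact 95% upper limit 1 − 0.025^(1/20) = 16.8%; one-sided 1 − 0.05^(1/20) = 13.9%.
- Chance of at least one event in an arm, 1 − (1 − p)^20, at assumed true rates: 64% at p = 5%, 88% at 10%, 99% at 20%.
- Fisher's exact test, 0/20 against b/20, two-sided p = 2·C(20,b)/C(40,b). For b = 4: 2 × 4,845/91,390 = 0.106. For b = 5: 2 × 15,504/658,008 = 0.047. At least five events against none are needed for p < 0.05.
- Exact power of Fisher's test at 20 per arm, rates assumed: 17% for 5% against 20%, 24% for 10% against 30%, 45% for 5% against 30%.

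The added rows can describe, with wide intervals, but they cannot test.

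**The case against.** The strongest reply is that little is lost. Potassium and sodium are measured and are secondary endpoints. The day-3 panel checks potassium for safety with no direction stated. The adverse event list is open, because it says only what it includes. All-cause hospitalization is a serious adverse event. Low values can be counted afterwards from data already planned, and in a 40-patient, seven-day pilot the counts would have little precision.

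Most of this stands. It would be wrong to say that low potassium or low sodium is not monitored, or that hypotension could not be recorded. Nor do the documents say that the secondary electrolyte endpoints will be analyzed only as continuous values, though that is the likely reading. But an open list permits recording without ensuring it. Hyperkalemia has a planned incidence, while low values depend on individual reports or an unplanned tabulation. The reply also leaves the missing day-7 blood pressure unanswered.

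Four stronger readings are tempting, and the documents do not support them.

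- *The whole safety comparison is tilted against the high dose.* The argument holds for potassium only. Leaving out low sodium and hypotension could favor the high dose, and creatinine, eGFR, death and hospitalization can move either way.
- *Many patients lose supplements or their home MRA.* Neither document says how many took either. The supplement hold applies only above 4.0 mmol/L, and both arms receive study spironolactone.
- *The data monitoring committee would see a one-sided picture.* The documents do not say what the committee receives, and the content of its stopping rule for harm is not given.
- *Counting both sides would remove any excess with the high dose.* This depends on assumed values. Take a normal distribution with SD 0.5 mmol/L, illustrative limits of 3.5 and 5.0, and arm means 0.6 apart. Means of 3.9 (25 mg) and 4.5 (100 mg) put about 23% and 18% out of range; means of 4.0 and 4.6 put about 18% and 23%. A shift of 0.1 mmol/L reverses the ranking. Adding the two tails also treats low and high potassium as equally harmful, which the documents do not establish.

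**Conclusion.** The point holds in a limited form. Both documents plan an incidence for high potassium only, although the treatment plan makes low potassium foreseeable and the randomized dose difference could reduce it. Low potassium and low sodium are measured but have no planned incidence by arm, and no blood pressure is stated after day 1. For potassium, the omission leaves out an event that could count in favor of the high dose; for low sodium and hypotension, the direction is not known.

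The size of any distortion cannot be calculated, because the documents give no event rates or potassium values by arm. The conclusion rests on reading the safety list as the full set of planned incidences, and on the ordinary expectation that more spironolactone retains more potassium. This is an inexpensive improvement to the safety reporting, not a flaw in the primary comparison.

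**What to change.** In the safety part of Study Endpoints, in both documents:

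1. Add the incidence by arm of hypokalemia and hyponatremia, from the day-3 and day-7 blood tests already planned. The investigators should fix the limits in advance, including the one for hyperkalemia, which is also not stated.
2. Tabulate potassium as low, normal or high by arm, so that both ends of the range appear together.
3. State a blood pressure reading at the existing day-7 office visit, and report hypotension by arm under a definition set in advance.
4. In the SAP, state that these are reported descriptively, as counts and percentages with exact intervals.
5. Include the same table in the safety data that the data monitoring committee reviews.

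The cost is a few more rows in the safety table and one reading at an existing visit. No new visit, blood sample or change to the sample of 40 is needed. The downside is more safety lines of low precision, which readers should not treat as tests.
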